To study the relationship between total number of reflux episodes, acid-, weakly acidic- and weakly alkaline reflux and GERD symptoms during 24 hours.

To study the pharmacokinetics of AZD3355 after 30, 90, 120 and 240 mg MR 1h capsules.

To study the relationship between exposure (area under curve (AUC)0-12h, AUC12-24h, AUC0-24h) and reflux episodes after the first and second doses of AZD3355.

Safety objectives

To assess the safety and tolerability of 4 different doses of AZD3355 as add-on treatment to a PPI, by evaluation of adverse events (AEs), laboratory variables, digital ECG (dECG) and physical examination.

To assess the effect of AZD3355 on orthostatic blood pressure and pulse, as well as sitting blood pressure and pulse over 24 hours.

Exploratory objectives

To collect and store DNA for future exploratory research into genes/genetic variation that may influence response (ie, PK profile, safety, tolerability and efficacy) to AZD3355 and/or susceptibility to GERD.

Study design

This is a randomised, double-blind, placebo controlled, 4-way crossover study to estimate the dose response relationship of AZD3355 on the number of reflux episodes assessed by esophageal impedance/pH monitoring in patients with GERD with a partial response to PPI treatment, as characterized by persistent GERD symptoms. Each patient will receive placebo and 3 of the 4 doses of AZD3355 in a randomised order.

Target patient population

Patients with GERD who have a partial response to PPI treatment, as characterized by persistent GERD symptoms.

Investigational product, dosage and mode of administration

AZD3355 30 mg, 90 mg, 120 mg or 240 mg MR1h capsule formulation taken orally twice daily.

Comparator, dosage and mode of administration

Placebo capsule to be taken orally twice daily.

Duration of treatment

The study starts with a pre-entry visit up to 21 day before treatment. This is followed by 4 treatment periods with a 7-28 days washout period between each. Each treatment period is one day, one dose in the morning and one dose in the evening. After the last treatment period the study ends with a follow-up visit 5-10 days later.

Outcome variable(s):

Primary Variable

Total number of reflux episodes (total, upright, supine).

Secondary Variables

Number and percentage of registration time of acid ($\text{pH} < 4$), weakly acidic ($4 \leq \text{pH} < 6.5$) and weakly alkaline ($\text{pH} \geq 6.5$) reflux episodes (total, upright, supine).

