1.3 Rationale for conducting this study

In a study in healthy volunteers ([D9120C00001](#)) an oral single dose of 0.8 mg/kg AZD3355 solution and placebo was given followed by a sleeve manometry combined with pH metry for 4 hours. A significant effect was demonstrated as compared to that of placebo, with a reduction of the number of TLESRs by 36% (95% CI 18% - 49%), an increase in the lower esophageal sphincter (LES) pressure as well as a reduction of acid reflux episodes.

In study [D9120C00020](#) in patients with persistent GERD symptoms despite PPI treatment, oral bid dosing of 65 mg AZD3355 (drug in capsule) and placebo was given as 3 doses (bid on day 1 and 1 dose in the morning of day 2) while impedance/pH registration was measured during 24 h, followed by a 4 h combined impedance/pH and manometric measurement on day 2. A significant effect compared to that of placebo was demonstrated, with an average reduction of TLESRs of 25% (geometric mean ratio 0.75 (95% CI 0.60, 0.93)). AZD3355 increased the LES pressure by 28% (geometrical mean ratio 1.28 (95% CI:1.05,1.57)). In the AZD3355 treatment group the mean value for the total number of reflux episodes was reduced by 10 (95%CI:-15, -4.8), which corresponds to a relative reduction of approximately 47%. During 24 hours post first dose the mean value for the total number of reflux episodes was reduced by 39% (geometric mean ratio 0.61 (95% CI:0.52, 0.71)) in the AZD3355 treatment group.

These studies explored only one dose level (0.8 mg/kg corresponds to a dose of 65 mg) however a dose response relationship in humans has not been determined. The present study therefore aim to explore the dose-response relationship and safety of both lower and higher doses of AZD3355 than tested in the previous efficacy studies (see above) in patients with GERD with a partial response to PPI treatment.

Further, blood will be collected for pharmacogenetic research to explore how genetic variations may affect the clinical parameters associated with AZD3355. Future research may

suggest other genes or gene categories as candidates for influencing not only response to AZD3355 but also susceptibility to Adverse Events for which AZD3355 may be evaluated. Thus, this genetic research may involve study of as yet un-named genes or gene categories.

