12.2 Methods of statistical analyses

The estimation of the dose-response curve will primarily be made by estimating the parameters of a fixed effect Emax model. In addition, the same model will be estimated with data from study [D9120C00020](#) (using 65 mg bid) included with a mixed effect Emax model with and without data from [D9120C00020](#) included. The possibility of using additional model will also be explored. The data will be logarithmically transformed prior to estimation of the dose-response curves. If zero values are obtained during a period then the logarithm is undefined and no transformation prior to analysis will be made. If the logarithmic transform is used the estimated mean curves and 2-sided 90% confidence interval (CI) limits will be transformed back to the original scale to give geometric mean curves and corresponding confidence intervals.

The effect of 4 different doses of AZD3355 measured as reduction in the total number of reflux episodes during 24 hours (total, upright and supine position), compared to placebo will be assessed by estimating the inhibition (%) in the primary variables after treatment with AZD3355 30 mg, 90 mg, 120 mg and 240 mg compared to placebo. Inhibition defined as $100 \times (1 - R)$ where R is the ratio (AZD3355/placebo) of estimated geometric means. The estimated geometric means for each treatment (AZD3355 30 mg, 90 mg, 120 mg and 240 mg and placebo) will also be presented. For estimating the geometric means the data will be logarithmically transformed prior to statistical analysis. If zero values are obtained during a period then the logarithm is undefined and no transformation prior to analysis will be made. Then the primary objective will be assessed by the differences in arithmetic means.

The analysis will be based on an mixed effect model with treatment, period and sequence as fixed effects and patient as a random effect. If the logarithmic transform is used the estimated arithmetic means and their differences and 2-sided 90% confidence interval (CI) limits will be transformed back to the original scale to give geometric means, ratios and corresponding confidence intervals. The same analysis will be made for the other variables addressed in the secondary objective.

No correction for multiplicity will be made.

Further details of the statistical analysis will be given in the Statistical Analysis Plan.

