12.3 Determination of sample size

In study [D9120C00020](#) the between and within-subject standard deviation (STD) for the logarithm of total number of reflux episodes during 24 hour ambulatory impedance monitoring was estimated to 0.79 and 0.25, respectively, using 21 evaluable patients. The geometric mean number of total number of reflux episodes was 30.6 (95% CI 20.9, 44.7) for AZD3355. This corresponded to a distance between the upper and lower 95% CI for the estimated mean of the logarithm of the total number of reflux episodes during 24 hours of 0.77. This precision was regarded as satisfactory.

By simulation of data with this variability, 20 patients and the treatment sequence used here, the width of the 95% CI for the estimated mean curve of the Emax model and the mixed effect Emax model was estimated to 0.70 and 1.73, respectively. When the data from [D9120C00020](#) was added to the simulated data, the width was estimated to 0.53 and 1.43, respectively. For a geometric mean of 30.6 these widths would correspond to 95% CI of (23.5, 39.9) and (15.0, 62.6), respectively.

With 20 randomised patients, all will be assigned to placebo, 14 will be assigned to AZD3355 30 mg, 16 will be assigned to AZD3355 90 mg, 16 will be assigned to AZD3355 120 mg and 14 will be assigned to AZD3355 240 mg. In order to achieving these numbers of evaluable patients on each of the doses the study will include 27 randomised patients.

The number of patients that will agree to participate in the genetic research is unknown. It is therefore not possible to establish whether sufficient data will be collected to allow a formal statistical evaluation or whether only descriptive statistics will be generated. A statistical analysis plan will be prepared where appropriate.

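### One zero count moves a variable from log ratios to arithmetic means and leaves its inhibition (%) undefined

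*Protocol*

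**What the plan says.** Section 12.2 plans to log-transform the data both for the Emax curves and for the comparisons of each dose with placebo. For each of the two it adds the same exception: "If zero values are obtained during a period then the logarithm is undefined and no transformation prior to analysis will be made". After the second statement it continues: "Then the primary objective will be assessed by the differences in arithmetic means". No minimum number or share of zeros is set, and no offset or count model is named.

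The effect measure is inhibition, 100 × (1 − R), "where R is the ratio (AZD3355/placebo) of estimated geometric means". No definition is given for untransformed data.

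The rule reaches several variables. The synopsis lists as primary variable "Total number of reflux episodes (total, upright, supine", and Section 12.2 asks for inhibition in all three. It then extends the method: "The same analysis will be made for the other variables addressed in the secondary objective". Section 2.2 includes acid, weakly acidic and weakly alkaline episodes there. The primary objective in Section 2.1 concerns the 24-hour total only.

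Section 12.3 bases precision on the log scale: the between- and within-subject SDs of the log total count "was estimated to 0.79 and 0.25, respectively, using 21 evaluable patients".

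**The concern.** A single observation can decide on which scale a variable is analysed and what quantity is estimated. The trigger is itself an outcome: zeros become more likely as reflux is suppressed, so the form of the answer depends on the effect being estimated. Once triggered, the rule yields a difference in mean counts, while the inhibition (%) that the protocol promises no longer has a definition for that variable. Counts meant to be read together (total, upright, supine, pH types) may then be reported partly as ratios and partly as differences. The fallback also assumes a common additive effect. With a between-patient log SD of 0.79 the counts are strongly skewed, and patients with high counts would dominate the estimate.

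**Working it through.** **Inputs from the protocol.** Section 12.3: between- and within-subject log SDs 0.79 and 0.25, 21 patients, and "The geometric mean number of total number of reflux episodes was 30.6 (95% CI 20.9, 44.7) for AZD3355". Section 1.3: "geometric mean ratio 0.61 (95% CI:0.52, 0.71" for the 24-hour total. Section 5.3.1: ten sequences of four periods. Section 12.3: 27 randomised to give 20 evaluable.

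**1. The plan's own figure.** The 95% CI width for the mean log count is 2 × 2.086 × √(0.79² + 0.25²)/√21 = 0.754. The printed limits give ln(44.7/20.9) = 0.760. The protocol states 0.77, so the SDs are usable. The placebo geometric mean follows as 30.6/0.61 = 50.2.

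**2. Chance of at least one zero.** Assumed model: count ~ Poisson(G × R_d × exp(b + e)).
- G is the placebo geometric mean.
- b has SD 0.79.
- e has SD 0.25, or 0.19 if counting noise is taken out (0.25² − 0.19² = 0.0264, the Poisson log-scale variance at a mean of about 1/0.0264 = 38).
- R_d is assumed to be 0.75, 0.60, 0.55 and 0.50 for 30, 90, 120 and 240 mg.

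I simulated 20,000 trials per setting on the ten sequences, with 80 or 108 patient-periods. Ranges run over the two values for e.

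| Placebo geometric mean | 20 patients | 27 patients |
|---|---|---|
| 50.2 (24-hour total) | 3.4–4.0% | 4.5–5.0% |
| 25 (assumed) | 24–26% | 31–33% |
| 15 (assumed) | 61–64% | 72–74% |
| 10 (assumed) | 88–90% | 95% |
| 5 (assumed) | over 99% | over 99% |

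The protocol does not say where the sub-counts lie, but they can be bounded. Geometric means of parts cannot add up to more than that of the whole. The smaller of upright and supine is therefore at most 50.2/2 = 25.1. The smallest of three pH classes, if they partition the total, is at most 50.2/3 = 16.7.

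**3. Dependence on the effect.** At G = 15 and SD 0.25 for e, the chance of a zero in one patient-period is 0.49% on placebo and 2.5% at the assumed ratio of 0.50, about five times as high.

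**4. Precision.** Information is taken as (mean estimate/its SD)², for raw differences relative to the ratio-scale analysis.

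For the 24-hour total in a paired comparison at R = 0.61:
- Log scale: (ln 0.61)²/(2 × 0.25²) = 0.2443/0.125 = 1.95.
- Raw scale, in units of the placebo geometric mean: squared mean difference 0.39² × exp(0.6866) = 0.302; variance 1.3721 × exp(1.3732) − 1.22 × exp(1.3107) − 0.302 = 0.590; ratio 0.51.
- Kept: 0.51/1.95 = 0.26.

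The same formula gives 0.50 at R = 0.9. Without patient terms, as in a plain fixed-effect fit, the figures are 0.63 and 0.69.

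For low counts a plain log analysis is impossible once zeros occur, so the comparator is a Poisson model conditional on patient (27 patients, R from 0.61 to 0.9):

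| Placebo geometric mean | Information kept by raw means |
|---|---|
| 15 | 0.64–0.91 |
| 10 | 0.67–0.95 |
| 5 | 0.83–0.95 |
| 2.5 | 0.91–1.0 |

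**The case against.** The best defence is that the primary objective is hardly touched. It concerns the 24-hour total, where a zero has a chance of about 3–5%; Section 2.2 treats upright and supine effects as secondary. The rule is prespecified and leaves no discretion. Arithmetic differences can also be informative: Section 1.3 reports from the earlier study a mean reduction of 10 episodes (95% CI −15 to −4.8) and expresses it as roughly 47%. Section 12.2 allows additional models and leaves further detail to the SAP.

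The point about the primary objective stands and limits the severity. The rest does not remove the defect. The protocol itself fixes the switch, and fixes it without saying what inhibition (%) means afterwards.

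Three stronger readings are tempting and are not supported:
- That one zero converts the whole analysis. Read naturally, the rule works variable by variable.
- That about half the information is lost. A figure near one half belongs to within-patient comparisons of the 24-hour total with small to moderate effects, and the total is the variable least likely to switch. It moves widely with effect and model.
- That zeros are known to be likely for supine or rarer types. The protocol gives no such counts.

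**Conclusion.** The concern holds for each variable that contains a zero: one outcome-dependent observation changes scale and estimand and leaves inhibition (%) undefined. Exposure is about 3–5% for the 24-hour total. For sparser counts it runs from about a quarter at a placebo geometric mean of 25 to about 90% or more at 10 or below.

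These chances assume that the SDs of the total carry over to sub-counts, that counts are Poisson given the patient-period mean, and that the dose ratios are as stated. More variable sub-counts would give more zeros, less variable ones fewer. Where switching is likely, the precision lost is about 0–36% and shrinks as counts fall. The main harm is therefore the changed estimand and mixed scales rather than lost power. Severity: should-fix.

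**What to change.** Keep the planned log analysis for every variable without zeros, including the 24-hour total as planned. In both places in Section 12.2, replace the switch to untransformed data, for count variables with zeros, by a prespecified ratio-scale analysis. This would be a log-link count model (negative binomial or over-dispersed Poisson) with treatment, period and sequence fixed and patient random, with Emax fitted on the log mean. Define inhibition there as 100 × (1 − rate ratio). Moving all counts to this model would go further than the defect requires.

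The cost is a change of wording and a standard mixed-model procedure, best settled before unblinding. The small downside is that those variables report a rate ratio instead of a ratio of geometric means. The two agree when the effect is a common multiplier and the log-scale variance is the same on drug and placebo.

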12.3 Determination of sample size

In study [D9120C00020](#) the between and within-subject standard deviation (STD) for the logarithm of total number of reflux episodes during 24 hour ambulatory impedance monitoring was estimated to 0.79 and 0.25, respectively, using 21 evaluable patients. The geometric mean number of total number of reflux episodes was 30.6 (95% CI 20.9, 44.7) for AZD3355. This corresponded to a distance between the upper and lower 95% CI for the estimated mean of the logarithm of the total number of reflux episodes during 24 hours of 0.77. This precision was regarded as satisfactory.

By simulation of data with this variability, 20 patients and the treatment sequence used here, the width of the 95% CI for the estimated mean curve of the Emax model and the mixed effect Emax model was estimated to 0.70 and 1.73, respectively. When the data from [D9120C00020](#) was added to the simulated data, the width was estimated to 0.53 and 1.43, respectively. For a geometric mean of 30.6 these widths would correspond to 95% CI of (23.5, 39.9) and (15.0, 62.6), respectively.

With 20 randomised patients, all will be assigned to placebo, 14 will be assigned to AZD3355 30 mg, 16 will be assigned to AZD3355 90 mg, 16 will be assigned to AZD3355 120 mg and 14 will be assigned to AZD3355 240 mg. In order to achieving these numbers of evaluable patients on each of the doses the study will include 27 randomised patients.

The number of patients that will agree to participate in the genetic research is unknown. It is therefore not possible to establish whether sufficient data will be collected to allow a formal statistical evaluation or whether only descriptive statistics will be generated. A statistical analysis plan will be prepared where appropriate.

13. IMPORTANT MEDICAL PROCEDURES TO BE FOLLOWED BY THE INVESTIGATOR

13.1 Medical emergencies and AstraZeneca contacts

The Principal Investigator is responsible for ensuring that procedures and expertise are available to handle medical emergencies during the study. **A medical emergency usually constitutes an SAE and is to be reported as such, see Section [6.4.4](#).**

The treatment code should not be broken except in medical emergencies when the appropriate management of the patient requires knowledge of the treatment code, see Section [5.5.2](#).

In the case of a medical emergency the investigator may contact the Study Delivery Team Leader. If the Study Delivery Team Leader is not available, contact the Study Delivery Team Physician.

Name	Role in the study	Address & telephone number

13.2 Overdose

A dose of AZD3355 in excess of that planned according to this protocol is to be considered an overdose. There are no data on overdosing. There is no known antidote. In case of known or suspected overdose, symptomatic treatment as well as close monitoring of vital functions should be carried out. This should be recorded as follows

- An overdose with associated AEs is recorded as the AE diagnosis/symptoms on the relevant AE modules in the CRF and on the Overdose CRF module.
- An overdose without associated symptoms is only reported on the Overdose CRF module.

If an overdose on an AstraZeneca study drug occurs in the course of the study, then investigators or other site personnel inform appropriate AstraZeneca representatives **within one day**, ie, immediately but no later than **the end of the next business day** of when he or she becomes aware of it.

The designated AstraZeneca representative works with the investigator to ensure that all relevant information is provided to the AstraZeneca Patient Safety data entry site.

For overdoses associated with SAE, standard reporting timelines apply, see Section 6.4.4. For other overdoses, reporting should be done within 30 days.

13.3 Pregnancy

All outcomes of pregnancy should be reported to AstraZeneca.

13.3.1 Maternal exposure

If a patient becomes pregnant during the course of the study investigational product should be discontinued immediately.

Pregnancy itself is not regarded as an adverse event unless there is a suspicion that the investigational product under study may have interfered with the effectiveness of a contraceptive medication. Congenital abnormalities/birth defects and spontaneous

miscarriages should be reported and handled as SAEs. Elective abortions without complications should not be handled as AEs. The outcome of all pregnancies (spontaneous miscarriage, elective termination, ectopic pregnancy, normal birth or congenital abnormality) should be followed up and documented even if the patient was discontinued from the study.

If any pregnancy occurs in the course of the study, then investigators or other site personnel inform appropriate AstraZeneca representatives **within one day** ie, immediately but no later than the **end of the next business day** of when he or she becomes aware of it.

The designated AstraZeneca representative works with the investigator to ensure that all relevant information is provided to the AstraZeneca Patient Safety data entry site within 1 or 5 days for SAEs, see Section 6.4.4 and within 30 days for all other pregnancies.

Since AZD3355 is a new drug, there is no information on its effects on foetus or newborn children. Consequently, women of childbearing potential can only be included if they are using a highly effective method of birth control (see recommendations in Section 5.2). Postmenopausal women (natural menopause with last menses >1 year ago and >50 years old) and women who are bilateral oophorectomised or hysterectomised are allowed to participate in the study.

The same timelines apply when outcome information is available.

13.3.2 Paternal exposure

There is no restriction on fathering children or donating sperm during the study.

Appendix B
Additional Safety Information

FURTHER GUIDANCE ON THE DEFINITION OF A SERIOUS ADVERSE EVENT (SAE)

Life threatening

‘Life-threatening’ means that the subject was at immediate risk of death from the AE as it occurred or it is suspected that use or continued use of the product would result in the subject’s death. ‘Life-threatening’ does not mean that had an AE occurred in a more severe form it might have caused death (eg, hepatitis that resolved without hepatic failure).

Hospitalisation

Outpatient treatment in an emergency room is not in itself a serious AE, although the reasons for it may be (eg, bronchospasm, laryngeal oedema). Hospital admissions and/or surgical operations planned before or during a study are not considered AEs if the illness or disease existed before the subject was enrolled in the study, provided that it did not deteriorate in an unexpected way during the study.

Important medical event or medical intervention

Medical and scientific judgement should be exercised in deciding whether a case is serious in situations where important medical events may not be immediately life threatening or result in death, hospitalisation, disability or incapacity but may jeopardize the subject or may require medical intervention to prevent one or more outcomes listed in the definition of serious. These should usually be considered as serious.

Simply stopping the suspect drug does not mean that it is an important medical event; medical judgement must be used.

Examples of such events are:

- Angioedema not severe enough to require intubation but requiring iv hydrocortisone treatment
- Hepatotoxicity caused by paracetamol (acetaminophen) overdose requiring treatment with N-acetylcysteine
- Intensive treatment in an emergency room or at home for allergic bronchospasm
- Blood dyscrasias (eg, neutropenia or anaemia requiring blood transfusion, etc) or convulsions that do not result in hospitalisation
- Development of drug dependency or drug abuse.

A GUIDE TO INTERPRETING THE CAUSALITY QUESTION

The following factors should be considered when deciding if there is a “reasonable possibility” that an AE may have been caused by the drug.

- Time Course. Exposure to suspect drug. Has the subject actually received the suspect drug? Did the AE occur in a reasonable temporal relationship to the administration of the suspect drug?
- Consistency with known drug profile. Was the AE consistent with the previous knowledge of the suspect drug (pharmacology and toxicology) or drugs of the same pharmacological class? OR could the AE be anticipated from its pharmacological properties?
- Dechallenge experience. Did the AE resolve or improve on stopping or reducing the dose of the suspect drug?
- No alternative cause. The AE cannot be reasonably explained by another aetiology such as the underlying disease, other drugs, other host or environmental factors.
- Rechallenge experience. Did the AE reoccur if the suspected drug was reintroduced after having been stopped? AstraZeneca would not normally recommend or support a rechallenge.
- Laboratory tests. A specific laboratory investigation (if performed) has confirmed the relationship?

A “reasonable possibility” could be considered to exist for an AE where one or more of these factors exist.

In contrast, there would not be a “reasonable possibility” of causality if none of the above criteria apply or where there is evidence of exposure and a reasonable time course but any dechallenge (if performed) is negative or ambiguous or there is another more likely cause of the AE.

In difficult cases, other factors could be considered such as:

- Is this a recognised feature of overdose of the drug?
- Is there a known mechanism?

Ambiguous cases should be considered as being a “reasonable possibility” of a causal relationship unless further evidence becomes available to refute this. Causal relationship in cases where the disease under study has deteriorated due to lack of effect should be classified as no reasonable possibility.

Clinical Study Protocol Appendix C

Drug Substance	AZD3355
Study Code	D9120C00032
Edition Number	1
Date	

**Appendix C
International Airline Transportation Association (IATA) 6.2 Guidance
Document**

LABELLING AND SHIPMENT OF BIOHAZARD SAMPLES

International Airline Transportation Association (IATA) classifies biohazardous agents into 3 categories (http://www.iata.org/whatwedo/cargo/dangerous_goods/infectious_substances.htm). For transport purposes the classification of infectious substances according to risk groups was removed from the Dangerous Goods Regulations (DGR) in the 46th edition (2005). Infectious substances are now classified either as Category A, Category B or Exempt. There is no direct relationship between Risk Groups and categories A and B.

Category A Infectious Substances are infectious substances in a form that, when exposure to it occurs, is capable of causing permanent disability, life-threatening or fatal disease in otherwise healthy humans or animals. Category A pathogens are eg, Ebola, Lassa fever virus:

- are to be packed and shipped in accordance with IATA Instruction 602.

Category B Infectious Substances are infectious Substances that do not meet the criteria for inclusion in Category A. Category B pathogens are eg, Hepatitis A, B, C, D, and E viruses, Human immunodeficiency virus (HIV) types 1 and 2. They are assigned the following UN number and proper shipping name:

- UN 3373 – Biological Substance, Category B
- are to be packed in accordance with UN3373 and IATA 650

Exempt - all other materials with minimal risk of containing pathogens

- Clinical trial samples will fall into Category B or exempt under IATA regulations
- Clinical trial samples will routinely be packed and transported at ambient temperature in IATA 650 compliant packaging (http://www.iata.org/whatwedo/cargo/dangerous_goods/infectious_substances.htm)
- **Biological samples transported in dry ice require additional dangerous goods specification for the dry-ice content**
- IATA compliant courier and packaging materials should be used for packing and transportation and packing should be done by an IATA certified person, as applicable

- Samples routinely transported by road or rail are subject to local regulations which require that they are also packed and transported in a safe and appropriate way to contain any risk of infection or contamination by using approved couriers and packaging / containment materials at all times. The IATA 650 biological sample containment standards are encouraged wherever possible when road or rail transport is used.

Clinical Study Protocol Appendix D

Drug Substance	AZD3355
Study Code	D9120C00032
Appendix Edition Number	1
